Appendix 3 Prohibited anti-arrhythmic and HR-lowering drugs

The following anti-arrhythmic and HR-lowering drugs (systemic administration) are prohibited during the up-titration period (i.e., from Day 1 until Day 14 included and during the first 14 days after re-initiation of study treatment) [see Section 5.2.3]:

- Adenosine
- Acebutolol
- Ajmaline
- Amiodarone
- Aprinidine
- Atenolol
- Azimilide
- Bepridil
- Betaxolol
- Bisprolol
- Bretylium
- Bunaftine
- Carvedilol
- Cibenzoline
- Disopyramide
- Dofetilide
- Dronedarone
- Encainide
- Esmolol
- Flecainide
- Ibutilide
- Ivabradine

- Lidocaine
- Lorajmine
- Lorcainide
- Metoprolol
- Mexiletine
- Morcizine
- Nadolol
- Phenytoin
- Pilocarpine
- Prajmaline
- Procainamide
- Propafenone
- Propranolol
- Quinidine
- Sotalol
- Sparteine
- Tedisamil
- Timolol
- Tocainide
- Vernakalant

This list is not exhaustive; other anti-arrhythmic or HR-lowering drugs are also prohibited during uptitration. In case of doubt, please discuss the use of any potential anti-arrhythmic or HR-lowering drug with the sponsor.

Treatment with any of these therapies is also not recommended during maintenance treatment with ponesimod (i.e., 20 mg) and should be considered with caution if an alternative medication cannot be used.

15 March 2022, page 159/216

EDMS-ERI-207656619

EudraCT 2016-004719-10

Confidential

Appendix 4 Adverse events of special interest

AEs of special interest will include the anticipated risks of treatment with ponesimod, and the events that may be related to MS comorbidities (e.g., seizures or stroke). The following safety areas were updated from Protocol version 6 onwards to include identified risks:

- Bradyarrhythmia occurring post-first dose
- Macular edema
- Bronchoconstriction
- Severe liver injury
- Serious opportunistic infections including PML
- Skin cancer
- Convulsions
- Unexpected neurological or psychiatric symptoms/signs (PRES, ADEM, atypical MS relapses)

A list of AEs of special interest (MedDRA preferred terms) will be defined in the SAP.

15 March 2022, page 160/216

EudraCT 2016-004719-10 EDMS-ERI-207656619

Confidential

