2 STUDY OBJECTIVES

2.1 Safety objectives

- To describe the long-term safety and tolerability of ponesimod 20 mg in subjects with RMS.
- To describe the effects of re-initiation of ponesimod treatment after interruption in subjects with RMS.

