Any cardiac events of potential clinical concern on Day 1 and on the first day of re-initiation of study drug must be assessed by the first-dose administrator for seriousness, reported to the principal investigator, and recorded on the AE page of the eCRF. In addition, the first-dose administrator should determine the need for medical management and assist the treating neurologist in deciding what actions should be taken on study treatment, if any. In these events, the first-dose administrator may consult with a cardiologist.

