5.1.2 Study treatment administration

5.1.2.1 Up-titration (performed by IVRS)

A gradual up-titration of ponesimod from a 2 mg starting dose to a 20 mg maintenance dose over a period of 14 days was found to successfully mitigate first-dose effects. This 2 week up-titration regimen will be implemented in the study on initiation of treatment (Day 1) and on days of reinitiation of treatment following treatment interruption of 4 days or more [see Section 5.1.9].

Confidential

Table 3 Dosing scheme

15 March 2022, page 64/216

Version 6

Treatment period	Duration	Dose regimen	Dose level
Up-titration	Day 1 and 2	2 mg	1 and 2
Up-titration	Day 3 and 4	3 mg	3 and 4
Up-titration	Day 5 and 6	4 mg	5 and 6
Up-titration	Day 7	5 mg	7
Up-titration	Day 8	6 mg	8
Up-titration	Day 9	7 mg	9
Up-titration	Day 10	8 mg	10
Up-titration	Day 11	9 mg	11
Up-titration	Day 12 to 14*	10 mg	12 to 14
Maintenance	Day 15 until EOT	20 mg	15 to 17*

^{* =} Visit 2 is to take place at Day 15 (1 / +3 day). The titration kit will therefore include 3 additional tablets (to be used if applicable) for treatment on Day 15-17 (i.e., dose regimen = 20 mg).

EOT = End-of-Treatment.

Study treatment up-titration, other than described above, is prohibited. Study treatment down titration is not foreseen in any situation and is prohibited.

One tablet will be taken orally o.d., preferably in the morning, either with breakfast or before or after breakfast, at approximately the same time each day. The tablet will be swallowed as a whole. The last administration date and time of study treatment prior to the study visits and the administration date and time of study treatment on the days of visits will be recorded in the eCRF.

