Other endpoints		
 Absolute values and change from baseline for HR, SBP, DBP and body weight at all assessments 	Y	Y
• Treatment-emergent notable blood pressure abnormalities##	Y	Y
 Absolute values and change from baseline for laboratory tests (hematology, blood chemistry, urinalysis) at all assessments 	Y	Y
• Treatment-emergent notable laboratory abnormalities##	Y	Y
 Change from baseline to EOS versus change from baseline to EOT in lymphocyte counts (absolute and percent change)** 	Y	N
• Treatment-emergent eC-SSRS suicidal ideation score of 4 or above, or a "yes" response on the eC-SSRS suicidal behavior item	Y	N

Cumulative safety data, i.e., AEs for the combined analysis period will only be presented for subjects who received 20 mg ponesimod in the core study.

The selection of AEs of special interest [see Appendix 4] is based on the anticipated risks of treatment with ponesimod; the final list of AEs of special interest will be defined in the SAP.

The selection of notable abnormalities considered for the analyses is based on standard definitions and the anticipated risks of treatment with ponesimod; the final list of abnormalities will be defined in the SAP.

^{**} Only for subjects who have no exposure to commercially available ponesimod prior to the EOS visit.

AE = adverse event; DBP = diastolic blood pressure; DL_{CO} = diffusing capacity for the lungs measured using carbon monoxide; eC-SSRS = electronic self-rated version of the Columbia-Suicide Severity Rating Scale; ECG = electrocardiogram; EOS = End-of-Study; EOT = End-of-Treatment; FEV_1 = forced expiratory volume in 1 second; FVC = forced vital capacity; HR = heart rate; QTcB = QT corrected for heart rate on the basis of Bazett's formula; QTcF = QT corrected for heart rate on the basis of Fridericia's formula; SAE = serious adverse event; SAP = statistical analysis plan; SBP = systolic blood pressure.

15 March 2022, page 89/216

Confidential

EudraCT 2016-004719-10 EDMS-ERI-207656619

The treatment-emergent period is defined as the time from first ponesimod administration in the applicable Analysis Period up to 15 days (inclusive) after last study treatment administration. This definition applies regardless of whether the subject receives commercially available ponesimod after completing study treatment.

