11.4.8.2 Cardiac safety

11.4.8.2.1 Treatment-emergent abnormalities

Treatment-emergent morphological ECG abnormalities will be summarized in a similar manner to AEs, and will include the cardiac safety events:

- Treatment-emergent QTcF >450 ms, >480 ms, >500 ms
- Treatment-emergent QTcF increase from baseline >30 ms, >60 ms
- Other treatment-emergent abnormalities observed by 12-lead ECG
- Treatment-emergent (serious) cardiac AEs of special interest.

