To ensure uninterrupted treatment, consider performing an early (unscheduled) study drug dispensation for your patients as soon as possible at your discretion ensuring that the material will not expire before the next scheduled visit. This is important since an interruption of ponesimod treatment may be associated with return of MS disease activity. Also, due to the known risk of bradyarrhythmia upon treatment re-initiation after an interruption of 4 days or longer, treatment must be restarted using the up-titration kit. If a patient is unable to travel to the site for a scheduled visit where study drug would be dispensed, the following alternate measures should be discussed with the sponsor and may be considered to ensure continuity of treatment:

- A caregiver or family member may pick up study drug on behalf of the patient if first discussed and agreed by the patient. The conversation with the patient must be documented in the source files. The patient must name the individual who will pick up study drug on their behalf. This is necessary for site staff to confirm the study drug is provided to the appropriate individual, ensure proper chain of custody of study drug, and to maintain patient privacy. This must be confirmed and documented in the patient source file.
- Investigative site staff may deliver study drug directly to the patient's home. The chain of custody and transit conditions must be clearly documented within the patient source file.
- If no other alternative is feasible, direct-to-patient shipment of study drug from the site may be considered with prior approval from the sponsor and relevant health authority, as applicable.
- It is important to remind patients that in case of treatment interruption of 4 or more consecutive days, they should inform the investigator and/or site staff immediately. Ponesimod treatment can only be restarted with up-titration and on-site cardiac monitoring, as applicable, as described in the protocol.

On-site Monitoring Visits:

In case on-site monitoring visits are not possible, your Site Manager may arrange remote site monitoring activities with you until the point at which regular on-site monitoring visits may resume.

SAE reporting should continue as usual until further notification through any of the following methods:

- Secure! email
- If secure email is not possible, please call your Site Manager or Local Trial Manager

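### The bradyarrhythmia area of special interest is worded for the first dose only and does not name re-initiation, which the protocol itself calls a known risk

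*Protocol*

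**What the plan says.** Appendix 4, updated in Version 6, lists eight safety areas of special interest. One concerns heart rhythm: "Bradyarrhythmia occurring post-first dose". It is the only one of the eight with a timing qualifier. The appendix closes with "A list of AEs of special interest (MedDRA preferred terms) will be defined in the SAP", and the notes to Table 9 in Section 6.2 add that "the final list of AEs of special interest will be defined in the SAP". Section 11.4.8.1.2, however, points to Appendix 4 as the place where the list is given.

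The second safety objective in Section 2.1 reads "To describe the effects of re-initiation of ponesimod treatment after interruption in subjects with RMS". The regional-crisis guidance at the end of the protocol requires the up-titration kit "due to the known risk of bradyarrhythmia upon treatment re-initiation after an interruption of 4 days or longer".

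On analysis, the cardiac summary in Section 11.4.8.2.1 includes "Treatment-emergent (serious) cardiac AEs of special interest" and so takes over whatever limit the area carries. Table 9 lists post-dose ECG change on Day 1 and on the day of re-initiation as an Extension Analysis Period endpoint. Section 11.4.8.2.3, which describes that analysis, covers only the day ponesimod is initiated in the extension.

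**The concern.** A category of special interest exists so that a named risk can be read off one table. Here the protocol identifies a risk at two kinds of occasion, first dosing and restarting, and words the category for the first only. A SAP that follows the wording would produce a special-interest table with no restart bradyarrhythmia, whatever happened in the study. A reader could take that for evidence of safe restarting, when it would only reflect the definition.

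Timing sharpens the point. Section 5.1.7 dates the last entry to the extension at 20 May 2019, and the Version 6 rationale of March 2022 says that no new patients will initiate treatment. From Version 6 on, the only new start-of-dosing exposure is re-initiation, which the wording does not name.

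**Working it through.** No arithmetic underlies the wording, so the check has three parts: what the phrase can mean, what each meaning does in each analysis period, and what other outputs show.

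**1. Possible meanings of the qualifier.**

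- *After the first dose only.* This is the literal reading. Restarts are outside.
- *Any time after the first dose.* Restarts are inside, but the qualifier then does nothing. Section 10.1.1 already starts treatment-emergence at the first ponesimod dose of the period.
- *After the first dose of each initiation or re-initiation.* Restarts are inside. But where the protocol means both occasions it names both. Section 5.1.2.1: "This 2 week up-titration regimen will be implemented in the study on initiation of treatment (Day 1) and on days of reinitiation of treatment". Section 3.4.4: "Any cardiac events of potential clinical concern on Day 1 and on the first day of re-initiation of study drug must be assessed". Table 9, Section 5.1.10 and Appendix 3 do the same. Appendix 4 names one.

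**2. The literal reading by analysis period.** Under Sections 11.4.8.1.1 and 11.4.8.1.2, events of special interest are summarised in two ways: over the Extension Analysis Period by core treatment and overall, and over the Combined Analysis Period for core-ponesimod subjects only. Section 10.1.1 sets the reference first dose in the extension for the former and in the core study for the latter.

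| Occasion | Combined Analysis Period | Extension Analysis Period |
|---|---|---|
| First-ever dose, core-ponesimod subjects | inside | not in this period |
| Extension Day 1, core-ponesimod subjects (14 to 44 days off drug, Section 3.2.3) | outside | inside |
| Extension Day 1, core-teriflunomide subjects | not summarised | inside |
| On-study restart after four or more missed days (Section 5.1.9) | outside | outside |

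**3. Size.** Section 11.6 expects about 800 entrants. Section 5.1.7 says roughly half of core subjects received teriflunomide. Assuming the same split among entrants, 800 × 0.5 = 400 core-ponesimod subjects restarted on extension Day 1. If the share were 45% to 55%, the range is 800 × 0.45 = 360 to 800 × 0.55 = 440. This figure applies to the Combined Analysis Period alone. The protocol gives no number of on-study restarts, so the part that is outside in both periods cannot be sized.

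**4. What other outputs show.**

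- Section 3.4.4 sends cardiac events of concern on the first day of re-initiation to the AE page, so they enter the AE and SAE tables of Section 11.4.8.1.1. Those tables are by system organ class, preferred term, intensity and relationship, with no split by first dose or restart.
- Section 11.4.8.2.1 also summarises other treatment-emergent ECG abnormalities without a first-dose limit. But Sections 5.1.9 and 7.5.1 let subjects without cardiovascular risk factors restart at home without post-dose monitoring. Where that option is used there is no post-dose tracing on the restart day.
- The Table 9 endpoint would show ECG change on the day of re-initiation, but Section 11.4.8.2.3 describes no analysis of it.

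So no analysis written in Section 11 isolates on-study re-initiation.

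**The case against.** The strongest reply is that the protocol nowhere excludes re-initiation and leaves the final list to the SAP, so an area heading is being treated as a counting rule. This stands in part: the SAP could settle the matter, and the phrase is open to more than one meaning. But Appendix 4 defers the preferred terms, and a list of terms does not by itself set timing relative to a dose. The qualifier is stated in the protocol, and a SAP that counted restarts would have to go beyond it. The protocol's own first-dose vocabulary does extend to re-initiation, since the first-dose administrator covers both, but that section names both occasions explicitly.

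A second reply is that nothing is lost, because the events are recorded and tabulated elsewhere. That is correct. A reader might infer that restart bradyarrhythmia goes uncounted in the study; Sections 3.4.4, 11.4.8.1.1 and 11.4.8.2.1 show otherwise. What is missing is its place in the special-interest summary and any label marking it as restart-related.

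A third reply is that the re-initiation objective names no event, and Section 1.4 describes the re-initiation question in terms of relapses and MRI lesions. This also stands, so the objective cannot be said to turn on bradyarrhythmia. Section 2.1 nevertheless files it under safety, and bradyarrhythmia is the restart risk that the protocol itself names.

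Finally, one might suppose that many restarts take place unmonitored at home. The protocol permits this for some subjects but documents no frequency, and Section 8.5.3 still requires a pre-dose assessment for everyone.

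**Conclusion.** The point holds as a wording defect with a definite effect on one summary. On the literal reading, on-study restarts are outside the bradyarrhythmia area in both analysis periods. Extension Day 1 of core-ponesimod subjects is outside it in the Combined Analysis Period only, which is about 400 restarts if entrants split evenly. For the Extension Analysis Period, Day 1 is covered and already split by core treatment.

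The conclusion rests on the literal reading of the qualifier, which fits the protocol's usage better than the alternatives but is not the only one possible, and on a SAP that has not been seen. It does not extend to a claim that the events are unrecorded or unreported. The mismatch between Table 9 and Section 11.4.8.2.3 needs no such reading: re-initiation appears in one and not in the other. The change is worth making before the analysis is fixed.

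**What to change.** - Reword the Appendix 4 area to: *Bradyarrhythmia occurring after the first dose or after any re-initiation*.
- Summarise first-dose and re-initiation events separately, and treat extension Day 1 of core-ponesimod subjects as a re-initiation in the Combined Analysis Period.
- Align Section 11.4.8.2.3 with Table 9, so that post-dose ECG change is summarised for the day of re-initiation wherever post-dose tracings were taken.

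The cost is one line in Appendix 4, the matching lines in Section 11.4.8.2.3 and the SAP, and a small extra table. AE dates and treatment interruptions are already recorded in the eCRF (Sections 3.4.4 and 5.1.8), so no new data are needed. No dose, monitoring rule or other clinical instruction changes.

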Appendix 5 Abnormalities for ECG, BP and laboratory variables

Notable abnormalities for ECG and BP that are related to the potential effects of ponesimod will address the following variables:

- Morphological ECG findings (defined as any abnormal finding not present prior to start of treatment).
- HR outliers (bpm), based on ECG
- PR interval (ms)
- QT/QTc interval (ms), QTcB or QTcF
- BP (mmHg)

The definition of the abnormal values to be reported will be described in the SAP.

Laboratory abnormalities

Laboratory values below or above the normal range will be graded at three levels (H, HH, HHH for values above normal range and L, LL, LLL for values below the normal range) where L stands for "low", H for "high".

The term "marked abnormality" describes laboratory values above or below the thresholds, with grading of abnormalities at two levels: LL/HH and LLL/HHH. These thresholds have been defined by the sponsor in order to flag and/or communicate abnormal laboratory results from the central laboratory to the investigators, and for the purpose of standardized data analysis and reporting by the sponsor. The definitions of marked abnormal values are based mainly on the Common Terminology Criteria for Adverse Events (CTCAE) [CTCAE 2010] grading system and, in specific cases (e.g., lymphocyte levels), are adjusted based on the known PD effect of the study treatments (e.g., LLL threshold for lymphocytes).

The term ALERT here corresponds to protocol-defined test result threshold requiring an action from the investigator as described in the protocol (e.g., repeat the test; interrupt or discontinue the study treatment) and should not be confused with the term "call alert" used by the central laboratory for laboratory results, which will be communicated to the investigator. Not all ALERTS listed in this table will be "call alerts" from the central laboratory and vice versa.

PLEASE NOTE: Thresholds for abnormality of level L or H are not provided in this appendix but will be provided in the central laboratory manual. Parameters for which no threshold is defined in Table 11 below may be defined in the central laboratory manual.

Confidential

Table 11 Thresholds for marked laboratory abnormalities

Parameter (SI unit)	LL	LLL	НН	ННН
Hemoglobin (g/L)	<100	<80	Increase in >20 g/L above ULN or above baseline (for pre-treatment assessments, and post-treatment assessments when baseline ≤ ULN) or increase from baseline >20 g/L (for post-treatment assessments when baseline is >ULN)	Increase in >40 g/L above ULN (for pre- treatment assessments, and post-treatment assessments when baseline ≤ ULN) or increase from baseline >40 g/L (for post-treatment assessments when baseline is >ULN)
MCH (pg/Cell)	ND	ND	ND	ND
MCV (fL)	ND	ND	ND	ND
Hematocrit (L/L)	<0.28 (female) <0.32 (male)	<0.20	>0.55 (female) >0.60 (male)	>0.65
Platelet count (10 ⁹ /L)	<75	<50	>600	>999
RBC count (10 ¹² /L)	ND	ND	ND	ND
WBC count (10 ⁹ /L)	NA	<1.9	>20.0	>100.0
Lymphocyte (10 ⁹ /L)	ND	<0.2 ALERT: <0.2	>4.0	≥8.0
Neutrophils (10 ⁹ /L)	<1.5	<1.0	ND	ND
Eosinophils (10 ⁹ /L)	ND	ND	>5.0	ND
Monocytes (10 ⁹ /L)	ND	ND	ND	ND
Basophils (10 ⁹ /L)	ND	ND	ND	ND
Polymorphonuclear leucocyte/Band cells (%)	ND	ND	>90%	>95%
AST (U/L)*	ND	ND	≥3 ULN	≥5 ULN
			ALERT:	ALERT:
			≥3 ULN	≥5 ULN
				≥8 ULN

Confidential

Parameter (SI unit)	LL	LLL	НН	ННН
ALT (U/L)*	ND	ND	≥3 ULN	≥5 ULN
			ALERT:	ALERT:
			≥3 ULN	≥5 ULN
				≥8 ULN
Total bilirubin (umol/L)	ND	ND	≥2 ULN	≥5 ULN
			ALERT:	The state of the s
			≥2 ULN combined with	
			ALT or AST ≥3 ULN	
Alkaline Phosphatase (U/L)	ND	ND	>2.5 ULN	>5 ULN
INR*	ND	ND	≥1.5 ULN	≥2.5 ULN
		11	ALERT:	
			≥1.5 combined with ALT or AST ≥3 ULN	
Lactate dehydrogenase	ND	ND	ND	ND
Creatinine (umol/L)*	ND	ND	>1.5 ULN or >1.5 × baseline	>3 ULN or >3 × baseline
Creatinine clearance (mL/min)	<60	<30	ND	ND
Urea (mmol/L)	ND	ND	>2.5 ULN	>5 ULN
Albumin (g/L)	<30	<20	ND	ND
Protein total (g/L)	ND	ND	ND	ND
C-reactive protein (mg/L)	ND	ND	ND	ND
Glucose (mmol/L)	<3.0	<2.2	>8.9	>13.9
Potassium (mmol/L)	<3.2	<3.0	>5.5	>6.0
Sodium (mmol/L)	ND	<130	>150	>155
Calcium (mmol/L)	<2.0	<1.75	>2.9	>3.1
Chloride (mmol/L)	ND	ND	ND	ND
Triglyceride (mmol/L)	ND	ND	>3.42	>11.4
Cholesterol (mmol/L)	ND	ND	>7.75	>12.92
Serum pregnancy test	ND	ND	ND	Positive
		***		ALERT:

CONFIDENTIAL - FOIA Exemptions Apply in U.S.

Ponesimod / ACT-128800 Relapsing multiple sclerosis Protocol AC-058B303, OPTIMUM-LT Version 6 15 March 2022, page 163/216

Confidential

EudraCT 2016-004719-10 EDMS-ERI-207656619

Parameter (SI unit)	LL	LLL	НН	ННН
				Positive
Teriflunomide (ng/mL)	ND	ND	ND	>20
				ALERT:
				>20

^{*} HH and HHH based on CTCAE 2010 v4.03 [CTCAE 2010]. An ALERT will be sent when INR ≥1.5 based on the guidance for monitoring liver test abnormalities from FDA [FDA 2009b]. Note: All events of ALT or AST ≥3xULN and total bilirubin ≥2xULN (>35% direct bilirubin) or ALT or AST ≥3xULN and INR >1.5 may indicate severe liver injury (possible 'Hy's Law') and must be reported to sponsor in an expedited manner and as an SAE if SAE criteria are met. The INR stated threshold value will not apply to participants receiving anticoagulants.

ALERT = study-specific alerts that trigger specific actions by the investigator [see Sections 5.1.12]; ALT = alanine aminotransferase; AST = aspartate aminotransferase; ND = not defined; may be complemented by definitions provided by the central laboratory (see central laboratory manual); ULN = upper limit of normal.

Confidential

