11.4.8.5 Laboratory endpoints

Descriptive summary statistics by visit will be provided for observed treatment-emergent values and absolute change from core baseline for laboratory tests (hematology, blood chemistry, urinalysis) by core study treatment for the Combined Analysis Period using the SAF. These parameters will also be summarized descriptively for the Extension Analysis Period by core study treatment and overall using the EXTS.

Treatment-emergent laboratory notable abnormalities will be summarized for subjects who received ponesimod 20 mg in the core study only for the Combined Analysis Period using the SAF.

The definition for notable abnormalities is provided in Appendix 5 and include:

- Treatment-emergent laboratory test abnormalities based on normal ranges of the central laboratory, project-specific ranges, and common terminology criteria for adverse events (CTCAE) [CTCAE 2010; see Appendix 5]
- Treatment-emergent laboratory test abnormalities based on FDA guidance for DILI [FDA 2009b] (for ALT / AST / total bilirubin).

Lymphocyte count reversibility after EOT will be summarized descriptively by comparing the mean (and 95% CIs) for absolute change in lymphocyte counts from core baseline to EOS, and from core baseline to EOT.** This analysis will be performed for the Combined Analysis Period by core study treatment using the SAF.

** applies only to subjects who have no exposure to commercially available ponesimod prior to the EOS visit.

11.4.8.6 eC-SSRS

The number and percentage of subjects with a treatment-emergent eC-SSRS suicidal ideation score of 4 or above, or a "yes" response on the eC-SSRS suicidal behavior item will be summarized descriptively by core study treatment for the Combined Analysis Period.

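### The hemoglobin HH cell in Table 11 can grade a value within or below the normal range as a marked high, contrary to Appendix 5's own grading rule and to the HHH cell

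*Protocol*

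**What the plan says.** The introduction to the laboratory part of Appendix 5 sets the general rule: "Laboratory values below or above the normal range will be graded at three levels (H, HH, HHH for values above normal range", with L, LL and LLL for values below it. HH and HHH, like LL and LLL, are called marked abnormalities. They serve both to flag results to investigators and to standardize the sponsor's reporting.

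The hemoglobin HH cell of Table 11 has two clauses. The first sets the threshold as "Increase in >20 g/L above ULN or above baseline" and applies it to pre-treatment assessments, and to post-treatment assessments when baseline is at or below ULN. The second reads "or increase from baseline >20 g/L (for post-treatment assessments when baseline is >ULN").

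The HHH cell has the same two-clause layout, but its first clause reads "Increase in >40 g/L above ULN (for pre- treatment assessments, and post-treatment assessments when baseline ≤ ULN"), with no reference to baseline. Change from baseline appears only in its second clause, for a baseline above ULN. The low side of the row is LL below 100 g/L and LLL below 80 g/L.

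Section 11.4.8.5 takes these thresholds into the analysis: "The definition for notable abnormalities is provided in Appendix 5 and include" abnormalities based on normal ranges, project-specific ranges and CTCAE. Treatment-emergent notable laboratory abnormalities are a safety endpoint in Table 9, whose footnote leaves the final list to the SAP.

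**The concern.** Both cells split subjects by whether baseline is above ULN. That split makes sense if a normal baseline is judged against ULN and a baseline already above ULN is judged by further rise. HHH does this. HH also lets a normal or low baseline be judged by rise alone, so a subject recovering from a low hemoglobin can be recorded as having a marked high one.

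At stake is the meaning of one row in a safety summary. Section 11.4.8.5 summarizes these abnormalities for the Combined Analysis Period only in subjects given ponesimod 20 mg in the core study, so no comparator group in that summary would show the background rate of such flags. Table 10 counts 26 hematology tests per subject, which gives a rise from a single baseline value many chances to exceed 20 g/L. The same thresholds are used for central-laboratory flags to investigators.

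**Working it through.** The protocol states no figure to reproduce. The check is first logical, then illustrative.

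**1. What the cell reduces to.** Let b be baseline, v a post-treatment value and U the ULN, all in g/L.

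- If b ≤ U, HH is met when v > U + 20 or v > b + 20. Because b + 20 ≤ U + 20, the first condition implies the second, and the trigger is v > b + 20.
- If b > U, the trigger is also v > b + 20.

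Both clauses become a rise of more than 20 g/L. The ULN limb and the split by baseline do nothing after treatment.

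**2. When a normal value is graded HH.** This needs b + 20 < v ≤ U, which is possible only if b < U − 20. With U assumed to be 160:

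| Baseline | HH trigger as written | Normal values graded HH | Trigger without the phrase |
|---|---|---|---|
| 105 | >125 | 125–160 | >180 |
| 125 | >145 | 145–160 | >180 |
| 135 | >155 | 155–160 | >180 |
| 140 or more (up to U) | >160 or higher | none | >180 |

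For b from U − 20 up to U, a flagged value is above ULN but may be less than 20 g/L above it.

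**3. An example that needs no assumed ULN.** A rise from 78 to 99 is 99 − 78 = 21 > 20, so it is HH. Since 99 < 100, it is also LL. One result is a marked low and a marked high.

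**4. HH beside HHH.** For b ≤ U, HH starts above b + 20 and HHH above U + 40, a gap of U − b + 20. With U = 160, the gap is 20 at b = 160 but 55 at b = 125. The two grades are not steps on one scale.

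**5. Pre-treatment use.** The first clause also covers pre-treatment assessments, yet Section 11.1.3 defines the safety baseline as the last value before first treatment. A comparison of pre-treatment values with baseline has no clear meaning there.

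**6. Possible frequency; every input is assumed.** Model A has 65% women, mean 133 (women) or 149 (men), between-subject SD 9, ULN 155 or 175, 24 post-baseline samples and no drug effect. Percent of subjects ever flagged HH:

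| Within-subject SD | As written | Also requiring v > ULN | Phrase deleted |
|---|---|---|---|
| 3 | 0.003 | – | – |
| 4 | 0.38 | – | – |
| 5 | 3.5 | 0.5 | 0.00 |
| 6 | 10.8 | 1.9 | 0.02 |
| 7 | 20.7 | 4.7 | 0.06 |

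Model B has mean 138, between-subject SD 11, a single ULN of 160, 25 post-baseline tests (26 in Table 10 less one) and the 800 subjects the protocol expects. For SD 4, 5, 6, 7 and 8 the subjects ever flagged number about 3, 29, 89, 167 and 250. Those with at least one flag on a normal value number 3, 23, 70, 126 and 184. With the phrase deleted the counts are 0, 0, 0.4, 1.5 and 3.5.

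A single-test check for SD s uses 1 − Φ(20/(s√2)). At s = 5 this is 1 − Φ(2.83) = 0.00234, against 0.00220 in the simulation, which also requires b ≤ U.

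**The case against.** The best defense is that the appendix's introductory rule governs the table: a value inside the normal range gets no H grade, so it cannot be HH, and the cell does no harm. But the protocol does not say that the introduction overrides a cell, and whoever programs the cell literally will flag these values. This reading shows one way to repair the cell; it does not remove the conflict.

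Second, the Table 9 footnote leaves the final list of abnormalities to the SAP, and Section 11.4.8.5 names several bases for them. That limits any prediction of what will be reported. It does not correct a threshold that Table 11 already fixes and that is also used for laboratory flags.

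Third, a baseline limb is not foreign to the table: creatinine is graded on a multiple of ULN or of baseline and can also reach an in-range value. That stands as a caution against calling the hemoglobin words an admitted slip. Creatinine, however, carries the limb in both HH and HHH, so its scale is consistent; hemoglobin changes reference between grades.

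A reader might also infer that many false highs will be reported, or that a real signal would be hidden. The documents support neither. They give no hemoglobin mean, variability or ULN, and the modeled rate almost vanishes at low within-subject SD. Hematology values and change from baseline are summarized by visit as well, and HHH is unaffected. No ALERT attaches to hemoglobin, so no protocol-mandated action follows from the cell.

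**Conclusion.** The point holds as an error in the text of Table 11. For a baseline more than 20 g/L below ULN, the HH cell can grade a value within or below the normal range as a marked high. That contradicts the grading rule of Appendix 5 and the parallel HHH cell, and it makes the ULN limb redundant after treatment. These conclusions follow from the wording and need no assumption.

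The size is uncertain. It runs from about 0% to about 21% of subjects ever flagged for within-subject SD 3 to 7 g/L in Model A, against under 0.1% without the phrase, and it rests wholly on assumed hemoglobin distributions. The effect is confined to one laboratory row in descriptive safety reporting and to central-laboratory flags. It is worth correcting because Section 11.4.8.5 draws its definition from this appendix.

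**What to change.** Delete *or above baseline* from the first clause of the hemoglobin HH cell. It then mirrors HHH: more than 20 g/L above ULN when baseline is at or below ULN, and a rise of more than 20 g/L from baseline only when baseline is above ULN. At minimum, require the value to exceed ULN. That ends the conflict with the introductory rule but leaves HH and HHH on different references. If a change-from-baseline grade was intended, the introduction to Appendix 5 and the HHH cell would both have to say so.

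Apply the chosen rule to core and extension data alike, and align the SAP derivation and the central-laboratory flag with it.

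The cost is one phrase, one derivation and one flag setting. The drawback is that hemoglobin HH counts may differ from core-study tables already produced; those should be re-run or the difference disclosed.
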